### 1.1.2 Radiation dose

Most of the trials listed in Table 1 used radiation doses of 30 Gy or more. In the German trial

published by Stuschke 1997, 26 Gy were mandatory for areas of possible microscopic disease and 36 Gy to macroscopic disease. In a multivariate analysis, a deviation of more than 20% of this dose proved to be a highly significant negative prognostic factor for recurrence [18].

In a 2011 published prospective British trial, the dose effect was evaluated in a randomized fashion in 361 patients with indolent lymphoma [23]. Patients received either 20 x 2 Gy or 12 x 2 Gy involved field radiotherapy. There was no difference in the local or systemic lymphoma control reported after median follow up of 5 years. However, some reservations have to be made: The patient cohort was very heterogeneous regarding the histology (40% non-follicular grade 1/2), the stage and pretreatment (30% were treated for recurrence), and the thoroughness of follow-up examinations (radiological and only clinical examinations were allowed) [23]. Despite this, 24 Gy has been recommended as a standard dose in England since the results of this study were published [24]. The German radiation oncology community is more concerned with the problems of the trial and has more confidence in the above mentioned data of Stuschke et al. suggesting a minimal dose of 36 Gy to macroscopic tumor sites [18].

However, low dose radiation therapy (LDRT) has shown long lasting effects. Ganem et al. published retrospective data about a low dose radiation therapy of follicular lymphomas in 1994 [25]. Twenty-seven patients with advanced disease were treated with 2 x 2 Gy over 3 days. A CR was achieved in 37%. More patients with low-grade lymphoma (according to the Working formulation) were treated subsequently using the 2 x 2 Gy scheme as published in 2001 by Girinsky et al.: Of 48 patients, 80% were pretreated with at least 2 different chemotherapy schedules in their past medical history. A total of 135 sites were treated using 2 x 2 Gy and this resulted in a 51% CR rate. Positive predictors were a lymphoma <5cm, less previous chemotherapies, and an age < 65 years [26].

Based on these data, a prospective multicenter phase 2 trial with 109 patients and recurrent indolent lymphoma was initiated and published by Haas et al in 2003 [5]. They reported a response rate of 92% and a CR rate of 61% (72% in patients without previous therapy). The local PFS in patients who achieved a CR was 75% after 2 years. The median local PFS was at 42 months.

Luthy et al. treated 33 patients with advanced or recurrent indolent lymphoma also using the 2 x 2 Gy schedule [27]. They described a CR rate of even 84%. However, they also reported 23% infield recurrences after a time of 9 months (median). Achievement of CR was not a positive predictor.

In summary, the CR rates after 2 x 2 Gy irradiation ranged between 37 and 84% (Table 2)

Table 2: Response (PR/CR) und rate of CR after 2 x 2 Gy IF radiotherapy (based on Luthy et al. [27])

Author	n	Total response [%]	CR [%]
Ganem, 1994 [25]	27	89	37
Sawyer, 1997 [28]	11	94	38
Girinsky, 2001 [26]	48	81	57
Johannsson, 2002 [29]	22	87	65
Haas, 2003 [5]	109	92	61
Luthy, 2008 [27]	33	95	84
Hoskin, 2014 [6]	243	80	48

The mode of action of 2 x 2 Gy is not completely understood. An induction of the p53 pathway is discussed [30]. Knoops et al. looked at lymph node biopsies before and after LDRT. They found an

upregulation of p53 expression in 10 of 15 samples. An increase of the p53 immuno-staining from 5% to >80% was seen in 7 samples [31]. This effect was observed primarily in the follicular lymphoma cells and not in T-cells or endothelial cells visible. In vivo imaging lead to the speculation, that LDRT neutralizes anti-apoptotic effects of the characteristic bcl-2 overexpression in follicular lymphoma cells [32].

The British FORT trial prospectively tested 12 x 2 Gy against 2 x 2 Gy in the treatment of indolent lymphomas in a randomized fashion. Recruitment was stopped shortly before the end of the trial was reached due to the superiority of the 24 Gy arm (freedom from local progression after 2 years 93.7% vs. 80.4%) [33]. The CR rate was 40% after LDRT (total response rate 74%) and 60% after 24 Gy (total response rate 81%). For follicular lymphomas, the final results showed a CR rate of 48% after LDRT and 68% after 24 Gy ( $p = 0.0096$ ). There were significantly more recurrences ( $n=70$ ) in the LDRT arm after a median follow-up time of 26 months as compared to the standard 24 Gy arm (21 recurrences; HR 3.42;  $p<0.0001$ ) [6]. However, this trial also has some major weaknesses [34]:

The inferiority regarding the PFS could have been strengthened by a possible imbalance between the two arms: There was no differentiation between follicular lymphoma grade 1, 2, 3a or 3b. A central review of the pathology confirmed only in 60% a follicular or a marginal zone lymphoma. There was no central pathological review in 20% of the patients and other lymphomas (also aggressive lymphomas) or no lymphoma at all were diagnosed in the other cases. It was not stratified after the size of the lesion. There was also no maximal size limitation and different response rates in relation to the size were not discussed. No difference in the PFS was seen in a subgroup analysis of all patients (4 Gy and 24 Gy), but there was no information about the effect of the different doses in respect to the size of the lesion. There was no information about previous and following treatments. In the staging and follow-up procedures, 3D imaging was not mandatory, conventional x-ray and clinical evaluations only were also allowed. It is not clear, how many of these patients were evaluated only clinically without 3D imaging. Unfortunately, there was also no information about the best response status of the patients with recurrence.

In summary, the FORT trial showed some effectiveness after LDRT, but it is not clear whether the difference between LDRT and 24 Gy was as large as published considering the above mentioned weaknesses.

### 1.1.3 Chemotherapy and radiation therapy

In the 70ties and 80ties, several trials addressed the possibility that relapse control could be improved by a combination of radiation therapy with systemic chemotherapy [35-38]. The sequential application of COP or CHOP-B and IF radiation therapy showed an improvement of the recurrence-free survival but not of the overall survival compared with historical data [39]. An update of the data revealed a 10 years recurrence free survival of 72%, which is superior to historical controls [40]. However, 22% of the patients developed a neutropenia grade IV and there were 14 secondary malignancies.

### 1.1.4 Immunotherapy using an anti-CD20-Antibody (MabThera / Rituximab)

In early and advanced stage CD20 positive follicular lymphoma, the use of the anti-CD20 antibody Rituximab has been evaluated as monotherapy or in combination with chemotherapy in several trials. The effectiveness of Rituximab without chemotherapy was tested in the SAKK 35/09 trial using two different dose schedules (4x vs. 8x) [41]. Most of the 202 included patients had an advanced disease, only 15% had a clinical stage I or II according to the Ann Arbor classification. Thirty-eight percent of the patients of the 8x arm showed a CR during follow-up. The highest CR rate was achieved in patients without previous chemotherapy in their medical history and 8 cycles of MabThera (52%) [41]. However, there was no plateau of the PFS curve in the long-term follow-up. The above-mentioned best subgroup had a PFS of 70% after 2 years and 45% after 5 years (median PFS 43 months) [42].

### 1.1.5 Combination of anti-CD20-antibody and radiation therapy

The MIR trial was a multi-center phase II trial investigating the combination of Rituximab with *involved field* radiotherapy in FL stage I/II patients [43]. The recruitment of 85 patients was finished in 2010. The final clinical results were presented on the annual meeting of the European Society of Therapeutic Radiation Oncology (ESTRO) 2014 in Vienna [4]: The effectiveness was comparable with the superior arm of the ARO98-01 trial (TLI) but with a lower morbidity profile. The PFS rate after 2 years was 86%. The CR rate after 4 cycles of MabThera (without radiation) was 29% in patients with macroscopic disease at inclusion. Best morphologic response was reached at month 6 with a CR rate of 79%. The final results are going to be published after integration of the scientific MRD data.

### 1.1.6 FDG-PET for staging and response evaluation

The sensitivity and specificity of a FDG-PET examination for staging purposes is very high [44-46]. Tskamoto describes a sensitivity of 91% in 193 regions with involvement of follicular lymphoma [45]. Only the involvement of the duodenum in 3 patients was not detected. Elstrom et al. reported of similar results (sensitivity 98% in 42 patients) [46]. A sensitivity of 98% and a specificity of 94% were presented by Wöhrer et al. in 62 patients with different grades of follicular lymphoma. These were lower if conventional staging methods were used (sensitivity 95%, specificity 80%) [44]. Luminari et al. looked at the consequences of an FDG-PET in 142 patients of the FOLL05 trial who were primarily staged by CT: Based on the FDG-PET, 32% more involved lymph node regions were detected (46/146). Less involved regions were diagnosed in 11%. A stage shift into a more advanced stage was diagnosed in 11% due to the FDG-PET [47].

The Cheson criteria of 2007 recommend FDG-PET for response evaluation in patients with Hodgkin's lymphoma or aggressive lymphomas [48, 49]. In these days, there was no statement for the use of FDG-PET for staging and response evaluation in indolent lymphomas due to the lack of consequences. However, it was recommended for clinical trials if the primary endpoint would be CR [48]. The current update from 2014 [50] includes now the use of FDG-PET for staging also for follicular lymphomas to avoid an "under staging" (up staging in 8-41%). The 5-PS score is recommended for interpretation of the results. The inclusion of FDG PET for staging also for follicular lymphoma was also based on the results of the PRIMA trial: A positive FDG-PET in the response evaluation showed to be a highly negative predictive value [7, 51]. Patients, who were PET negative after induction chemotherapy had a significant higher PFS after 42 months than PET positive patients (71% vs. 33%;  $p < 0.001$ ). The PET signal was an independent prognostic marker. Similar observation were made in the Italian FOLL05 trial [52]: PET negative patients had a significant superior PFS after 3 years compared to PET positive patients (66% vs. 35%,  $p < 0.001$ ). Looking only at the morphologic changes via CT, the prognostic difference between CR and non-CR was much weaker (3-years PFS 63% vs. 51%;  $p = 0.04$ ). The prognostic value was highest in case of a negative FDG-PET and a morphological PR in the CT scan [52].

## **1.2 Rational for the Current Trial Concept**

The MIR trial has shown that the radiation volumes could be significantly reduced without compromising the effectiveness of the historical large field irradiation. The toxicity of the combined approach of an anti-CD20 antibody and an *involved field* radiotherapy was much lower than the historical data of large field irradiation. Therefore, the combination of an anti-CD20 antibody with small field irradiation of the involved sites will probably become the new standard in the treatment of early stage nodal follicular lymphoma grade 1 and grade 2.

### Low dose radiation therapy

After the reduction of the radiation field, a marked reduction of the radiation dose should be tested prospectively: the combination of an anti-CD20 antibody and low dose radiation therapy (LDRT). Although the FORT trial resulted in an inferiority of LDRT compared to higher dose irradiation, it also showed effectiveness in part of the patients with follicular lymphoma (CR rate 48%).

In the GAZAI trial, the concept of LDRT with 2x2 Gy will for the first time be evaluated prospectively in a homogenous cohort of newly diagnosed, non-pretreated, and strictly examined FL grade 1 / 2 stage I/II patients. All diagnoses will be confirmed by central histological review. Involved-site irradiation will be combined with immunotherapy with an improved anti-CD20 antibody (Gazyvaro) with the aim to control occult systemic disease and prevent distant relapse. Additionally, there will be a precisely defined salvage option for those patients who do not achieve CR after the combined LDRT and antibody treatment. These patients will receive additional radiation therapy with 36 Gy (5x2 Gy/week) adding up to a total of 40 Gy which was the established dose of the MIR trial. This salvage dose is, therefore, response adapted for those patients who do not sufficiently respond to LDRT.

### Role of FDG-PET

The routine staging diagnostic procedures using CT/MRI will be augmented by a FDG-PET/CT examination in the GAZAI trial. The total radiation dose will then be defined response adapted by a second FDG-PET.

Since the sensitivity and specificity of FDG-PET is higher compared to sole morphological imaging, all patients will get an initial FDG-PET/CT. This has to be performed at least 5 weeks after a surgical procedure (e.g. lymph node sampling) for minimizing the risk of false positive results.

LDRT alone of the involved lymph nodes regions results in responses shown in Table 2. However, LDRT alone leads less often to a CR than a full dose radiation therapy in these patients (see Table 1 and 2 and the FORT trial).

Since a negative FDG-PET is an independent predictive factor regarding PFS [7, 51], the decision for or against salvage radiation will be done based on a restaging FDG-PET/CT (FDG-PET positive: salvage RT of additional 18 x 2 Gy; FDG-PET negative: no salvage RT).

Since only patients with initially PET positive lymph nodes are valuable for the evaluation of the primary endpoint (metabolic CR rate after LDRT and anti-CD20 antibody), the FDG-PET in week 18 can be omitted in case of FDG-PET negativity at the initial staging (e.g. all macroscopic pathological lymph nodes were surgically removed).

### Obinutuzumab (Gazyvaro)

The additional use of Rituximab in the radiation treatment of the early stages of nodular follicular lymphomas has been successfully proven in the MIR trial. However, Rituximab is a chimeric antibody and known to induce allergic reactions. One patient in the MIR trial could not complete the treatment due to an allergic reaction to Rituximab. It will, therefore, be useful to use a third generation humanized antibody instead.

Obinutuzumab is a humanized anti-CD20 antibody, which has already been approved for the treatment of CLL: Obinutuzumab showed superior results compared to Rituximab in an interim analysis of a prospective randomized trial [53, 54].

In follicular lymphoma, Obinutuzumab showed improved response rates in phase II trials if compared to Rituximab [55, 56]. A prospective randomized trial comparing Rituximab and Obinutuzumab in combination with a chemotherapy has completed recruitment. Just recently, primary results of the GADOLIN trial for Rituximab in refractory or fast recurrent follicular lymphoma resulted in the EMA registration of Gazyvaro in combination with Bendamustin chemotherapy. The combination of Bendamustin with Gazyvaro resulted in a 52% risk reduction for recurrence or death compared to Bendamustin alone [8, 57].

Based on these results, it can be assumed that the use of Obinutuzumab may induce a higher CR rate compared to the Rituximab data of the MIR trial. It might be, therefore, an ideal partner for LDRT and should reduce the portion of patients who need salvage RT. Additionally, QLQ data and MRD data can be used for historical comparison with the use of Rituximab in the MIR trial.

### 1.3 Benefit-/ Risk-Assessment

The standard treatment for the early stages of follicular lymphoma is under permanent discussion. Treatment recommendations range from watch & wait (with deferment of treatment until progression) to large field irradiations. The combination of *involved-field* irradiation and use of MabThera becomes more and more popular after the successful completion of the MIR trial. This includes an off-label use of MabThera, which is only accredited in the combination with chemotherapy for the treatment of follicular lymphoma.

The actual trial offers the chance of a substantial reduction of the radiation time (2 instead of 20 fractions in the best case) and the radiation dose (10% of the radiation dose in the best case). In any case, no patient will receive a higher radiation treatment dose compared to the dose of the MIR trial.

In addition to and in comparison with the MIR trial, the patients are treated with a humanized CD20 antibody with less allergic potential, receive only 7 instead of 8 administrations, and a potentially more efficient antibody as shown in CLL.

The use of LDRT has a higher risk of recurrence compared to a higher radiation dose according to the FORT trial. This risk will be minimized by additional salvage radiation up to the "full dose" in case of a failure to reach a complete remission. The use of FDG-PET/CT strengthens the initial staging and the evaluation of the response. The remaining risk of a late *in-field* recurrence after Obinutuzumab and LDRT has to be balanced against the substantially reduced radiation dose to the patient. In addition, "full dose" radiation therapy is still possible in case of a late recurrence.

### 1.4 Additional Scientific Project

The members of the pathology panel of the GLSG will conduct the pathological scientific add-on project. Genetic and molecular examinations of the already excised lymphoma specimen will be tested for different subgroups, which might result in the generation of new hypothesis [58, 59]. The genetic and molecular research strictly limited to all aspects of the lymphoma disease. The detection of certain genetic profiles, which might predict the response to LDRT is one of the goals of these studies.

### 1.5 Committees

The following committees were initiated to control certain aspects during the course of the trial:

#### 1.5.1 Data Monitoring Committee (DMC)

The DMC consists of independent experts in the treatment of malignant lymphomas. The DMC should evaluate the conduct of the trial, the safety, and the achievements of the major endpoints. The duty of the DMC is to secure the ethically correct conduct of the trial and to protect the interests of safety for the patients.

The DMC will meet on a regular basis (GLSG annual meetings). The DMC will give recommendations to the LKP regarding modifications, stopping or continuation of the clinical trial. Those recommendations should be sent to the LKP in written form within 2 months after the meeting. The DMC will get the annual DSURs.

The members of the DMC are listed in the protocol.

### 1.5.2 Steering Committee (SC)

The steering committee is comprised of the coordinating investigator and his supporting co-investigators, clinical experts not directly involved in the clinical trial, and the responsible biometrician. The steering committee is responsible for the scientific integrity of the study protocol, the quality of the study conduct as well as for the quality of the final study report. The Steering committee will decide on the recommendations made by the DMC. Members of the steering committee are listed in the protocol.

## **2. OBJECTIVES AND ENDPOINTS**

### **2.1 Study Objectives**

The rate of metabolic CR after low-dose radiotherapy in combination with Gazyvaro (Obinutuzumab) for early stage nodal follicular lymphoma will be assessed. In addition, the feasibility of a response adapted approach using FDG-PET/CT regarding success (PFS, rates of remission, analysis of recurrences) and safety in combination with Gazyvaro will be assessed.

The results will be historically compared to the results of the MIR trial regarding morphologic response in week 7 and the quality of life (secondary endpoints). Additional secondary endpoints are PFS, the site of recurrences in the three subgroups (1. PET negative after initial staging; 2. PET negative in week 18; 3. PET positive in week 18).

### **2.2 Primary Endpoint**

- Metabolic complete response (CR) in week 18 in patients with initially remaining lymphoma judged by FDG-PET/CT

### **2.3 Secondary Endpoints**

- Morphologic CR, PR, SD, PD in week 7, week 18 and month 6 in patients with initially remaining lymphoma judged by CT/MRI
- Historical comparison of the morphologic response with MIR data (using MabThera); The comparison of the CR rate in week 7 will allow for a comparison of the two different CD20 antibodies. Due to the restricted patient numbers no matched pair analysis will be possible
- Progression free survival (PFS) of all treated patients (2 years after individual treatment start)
- Toxicity (NCI-CTC criteria, version 4.03) of all patients
- Relapse rate and pattern of recurrence of all treated patients at all follow-up visits.
- Overall survival (OS) of all treated patients (2 years)
- Quality of life according EORTC QLQ C30 and FACT-Lym questionnaires at inclusion and in week 18, month 12, and 24 (all treated patients)
- MRD response in peripheral blood: initially, week 18, months 6, 12, 18 and 24 (all treated patients). MRD is evaluated by the laboratory of [name] (Kiel) using at least the markers: t(14:18) PCR for MBR, 3'mbr, 5'mcr and MCR; clonal IGH rearrangements (FR1-3); clonal IGL rearrangements (IGK and Kappa-KDE)

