**Background**

Large field radiation therapy has proven to be superior to more limited fields radiation in early stage follicular lymphoma in prolonging PFS (ARO 98-01 trial, personal communication [name])

The MIR trial showed, that at least in the short time follow-up, the addition of MabThera to a small-field radiation therapy in conventional dosage can lead to at least equal results concerning the PFS as compared to the historic large field data of the ARO 98-01 trial. However, the toxicity has been shown to be lower (Herfarth et al. 2014).

The metabolic CR rate as demonstrated by FDG-PET was identified as a prognostic marker for freedom of recurrence in advanced stage of follicular lymphoma (Trotman et al. 2011 PRIMA trial).

Immune modulating radiation therapy alone using a low-dose of 2 x 2 Gy (LDRT) has been shown to be effective in inducing CR in about 60% of follicular lymphoma in a prospective trial (Haas et al 2003) or 48% in the British FORT trial (Hoskin et al. 2014). It can be speculated that a CR-reponse to LDRT identifies specific subtypes of follicular lymphoma. Also, it is not known whether a combination of LDRT with anti-CD20 antibody therapy may enhance the CR-rate.

The goal of the current trial is a further reduction of the radiation dose in patients with a good response to a combination of LDRT and anti-CD20 immunotherapy. The shift from MabThera to Gazyvaro might lead to an even more effective treatment, which can be proven by the morphological response in week 7 and the MRD eradication in comparison to the MIR trial. Patients with insufficient response (no metabolic CR) after LDRT will receive an additional radiation dose of 36 Gy adding up to the total dose 40 Gy of the MIR trial.

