**Design of the trial**

Open, non-controlled, national multi-center phase II trial

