# 11. STATISTICAL PROCEDURES

## 11.1 Number of Patients

Due to the descriptive character of the trial, no assessment of any formal statistical hypotheses is performed. The calculation of the number of patients is primarily based on the aspects of practicability and precision of the results. The following calculations are based on the intention-to-treat (ITT) population. Since the strength of the results for the primary endpoint may be weakened due to early drop-outs (as described later), the number of patients needed should be high enough to compensate for potential drop-outs. Primary endpoint is the rate of metabolic CR in week 18 in patients with initially remaining lymphoma judged by FDG-PET/CT. Based on the morphologic CR rate of 37-84% after 2 x 2 Gy in the literature (see Table 2) and in face of a lack of data for metabolic CR after 2x2 Gy, a CR rate of 60% (about the median of CR in Table 2 and approximately the CR rate in week 18 in the MIR

trial (62%)) is assumed. If fifty patients enter the FDG-PET/CT and the observed metabolic CR rate amounts to 60%, the half width of the asymptotic two-sided 95% confidence interval amounts to about  $\pm 13.5\%$ .

Based on the experience of the MIR trial, a general drop-out rate of 10% is assumed, and about 30% of the included patients are expected to have no remaining lymphoma after initial surgery to prove the histology. In addition, we expect an additional drop-out rate of about 15% after the initial FDG-PET due to stage-shifting in a stage III disease based on the Barrington paper about PET staging [45].

These considerations lead to the following calculation:

If 93 patients are being recruited, about 15% will drop out due to a stage-shift to higher stages after FDG-PET (79 patients remaining). Of these 79 patients, about 30% will have no remaining PET-positive lymphoma after initial surgery (according to the experiences in the MIR trial). Therefore, 55 patients would start therapy with the goal of reaching the primary endpoint assessment. Assuming a drop-out rate of 10%, 50 patients will be available for final assessment of the primary endpoint.

The number of  $n=93$  is at the upper limit of the patients to be included. This number of definitively included patients might drop during the trial (e.g. if less patients show a stage-shift or more patients show remaining lymphoma).

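### The week-7 CR comparison with MIR is presented as a comparison of the antibodies, even as proof, but it is an unadjusted historical contrast with no interval planned for the difference.

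*Combined protocol and SAP*

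**What the plan says.** The week-7 comparison with MIR is a named secondary endpoint. Section 2.3 states: "The comparison of the CR rate in week 7 will allow for a comparison of the two different CD20 antibodies". The secondary endpoints in the Synopsis and in section 11.2 carry the same sentence with small changes. The Synopsis background goes further. It says the switch of antibody might give a more effective treatment, "which can be proven by the morphological response in week 7 and the MRD eradication in comparison to the MIR trial".

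Other parts of the plan limit what such a comparison can show:

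- The design is described as "Open, non-controlled, national multi-center phase II trial".
- Section 11.1 says "no assessment of any formal statistical hypotheses is performed".
- Section 2.3 rules out matching: "Due to the restricted patient numbers no matched pair analysis will be possible". No other adjustment is named.
- Section 11.4 reports remission rates with Wilson 95% intervals. It names no method for the comparison with MIR and no interval for a difference.

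The benchmark is in section 1.1.5: "The CR rate after 4 cycles of MabThera (without radiation) was 29% in patients with macroscopic disease at inclusion". No count is given with it. On staging, section 1.2 (Role of FDG-PET) says that routine CT/MRI "will be augmented by a FDG-PET/CT examination in the GAZAI trial", and section 11.1 expects about 15% of recruited patients to leave before therapy because PET moves them to a higher stage.

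**The concern.** The week-7 reading is the plan's stated basis for judging the change from rituximab to obinutuzumab. The choice of time point is sensible, because it follows four antibody infusions and precedes radiotherapy. But the two rates come from different trials, run one after the other, with no concurrent control and no adjustment. Patient selection, staging, imaging and the denominator can all differ alongside the drug.

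Two consequences follow. First, a reader of the final report could take a higher rate as evidence about the antibody, because the protocol says it allows that comparison. Second, the only interval planned is for the GAZAI rate. Set beside 29% as if that were a known constant, it understates the uncertainty, because MIR's sampling error is left out.

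**Working it through.** **The plan's own precision figure.** Section 11.1 uses 50 patients and a 60% rate: 1.96 × √(0.60 × 0.40 / 50) = 0.136, or ±13.6 points against the stated ±13.5. The patient flow also reproduces: 93 × 0.85 = 79; 79 × 0.70 = 55; 55 × 0.90 = 49.5, about 50. No precision is stated for the week-7 comparison.

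**Inputs for the week-7 comparison.**

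- MIR rate: 29% (section 1.1.5).
- MIR denominator: not given. MIR had 85 patients (section 1.1.5), and section 11.1 attributes to MIR a share of about 30% without remaining lymphoma. So 0.70 × 85 = 59.5, taken as 60. This is an assumption; the range 50 to 85 is shown.
- GAZAI number: 55 (section 11.1). This is the PET-positive count, so the number with macroscopic disease on CT/MRI may differ.

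**Precision of the difference.** Half-width = 1.96 × √[0.29 × 0.71 × (1/55 + 1/n)], with both rates at 29%:

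| MIR n | 95% half-width |
|---|---|
| 50 | 17.4 points |
| 60 (assumed) | 16.6 points |
| 85 | 15.4 points |

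If 29% is treated as fixed, the half-width is 1.96 × √(0.29 × 0.71 / 55) = 12.0 points. Ignoring MIR's sampling error thus narrows the interval from about ±17 to about ±12. The benchmark alone is loose: 17/60 (28.3%) has a Wilson interval of 18.5% to 40.8%.

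**Why this matters in practice.** Suppose GAZAI observed 24/55 (43.6%). Its Wilson interval is 31.4% to 56.7%, which excludes 29% and would look convincing beside it. Against 17/60, the difference is 15.3 points, and the score-based (Newcombe) 95% interval runs from −2.2 to +31.7 points, which includes zero.

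**Possible effect of PET staging.** Let s be the share removed by PET and q the week-7 CR rate those patients would have had. With identical drugs, a 29% rate in the CT/MRI-staged population becomes (0.29 − s·q)/(1 − s) after removal. At s = 0.15:

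| q | Rate after removal | Shift |
|---|---|---|
| 29% | 29.0% | 0 |
| 14.5% | 31.6% | +2.6 points |
| 0% | 0.29/0.85 = 34.1% | +5.1 points |

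This assumes that MIR was not PET-staged, that the 15% applies equally to patients with macroscopic disease, and that upstaged patients respond no better than the rest.

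**Was MIR PET-staged?** The documents do not say. Section 1.1.5 has MIR recruitment ending in 2010. Section 1.1.6 says the 2007 criteria were silent on PET staging in indolent lymphoma and that the 2014 update added it for follicular lymphoma. Section 1.3 presents PET/CT as strengthening the initial staging. Section 11.1 takes the 15% from a staging publication and adds it to the MIR-based rates. Together these suggest MIR was not staged this way, but that is an inference.

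**Which denominator?** The term for remaining lymphoma is used in several senses. The Study Flow Chart and section 11.1 tie it to PET positivity. Section 8.1.4 has a category of PET-negative remaining lymphoma. Section 11.6 allows either morphologic or metabolic. In section 2.3 the reference to CT/MRI can be read as describing the response or the population. MIR's 29% is for macroscopic disease at inclusion.

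**The case against.** The strongest reply is that the plan is modest where it counts. The endpoint is headed as a historical comparison, admits that matching is impossible, and sits in a trial declared descriptive. The proof wording is background prose and is hedged. Section 11.4 already gives the GAZAI rate a Wilson interval, and a separate SAP is still to be finalized before database lock. No treatment decision, stopping rule or sample size rests on this comparison, and week 7 isolates the antibody from radiotherapy in both trials.

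Much of this stands, and it sets the size of the point. It does not remove it. The hedge concerns whether a benefit exists, not whether this comparison could prove one. Isolating the antibody from radiotherapy does not isolate it from differences between the trials. And an interval for one rate is not an interval for a difference.

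Four stronger readings are tempting and should not be drawn:

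- That the plan claims superiority. It never uses that word; it speaks of a more effective treatment and of proof.
- That the week-7 denominator is PET-positive patients and so differs from MIR's. The wording is inconsistent, and the CT/MRI reading in section 2.3 is at least as natural.
- That the trials were staged differently as a matter of fact. MIR's staging is not described.
- That PET staging alone moves 29% to 34%. That is the ceiling, reached only if no upstaged patient had a CR. Week-7 response is read on a CT of the involved region (Study Schedule, footnote 17), so a distant lesion seen only on PET need not prevent a CR there.

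**Conclusion.** The point holds as one of over-strong interpretation and a missing measure of uncertainty. A difference from MIR in week-7 CR cannot on its own be attributed to the antibody, and it cannot prove greater effectiveness. On the plan's numbers the difference would be known to about ±15 to 17 points, assuming 55 GAZAI patients, 50 to 85 MIR patients and rates near 29%. Stage migration is the smaller part: 0 to about 5 points at the planned 15% shift, and only if MIR was not PET-staged. It could not explain a very large difference. The primary endpoint is unaffected, so this is a minor-to-moderate point.

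**What to change.** 1. In the Synopsis background, delete the clause that says greater effectiveness can be proven by comparison with MIR.
2. In the Synopsis endpoints, section 2.3 and section 11.2, describe the week-7 result (after four antibody infusions and before radiotherapy) as an exploratory, descriptive historical comparison that cannot by itself be attributed to the antibody. Change all three places together.
3. In section 11.4 and the SAP, report the difference in week-7 CR rates with a 95% score-based interval that includes MIR's sampling error, using MIR's actual numerator and denominator.
4. State that the week-7 denominator is macroscopic disease on CT/MRI at inclusion, to match MIR.
5. Add a sensitivity range of 29% to 34% for the historical rate, with 34% labelled as an upper-bound scenario. If MIR turns out to have been PET-staged, drop it.

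The cost is wording, one extra table and retrieval of MIR's count. On the GAZAI side the baseline CT/MRI and the week-7 CT are already scheduled. The claim becomes more modest.
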